8.2 Medically-Attended Events and Significant New Medical Conditions

These classes of events will be collected at all study visits, and if offered spontaneously by the subject at any time.

MAEs are adverse events which result in an unscheduled visit to a healthcare provider due to symptomatic illness or injury. These may include office visits, clinic visits, home consultations, or emergency room evaluations for non-life-threatening events that do not result in hospitalization (life-threatening events or hospitalizations are SAEs, see Section 8.2 of the protocol).

SNMCs are adverse events that are new (that is, not present at baseline), clinically significant (meaning that they imply an important change in the subject's long-term health status), and

typically chronic (requiring an ongoing change in the subject's medical management). This category is not meant to include minor or transient diagnoses or age-related changes. For example, while new diagnoses of presbyopia or tinea versicolor are chronic conditions, they are not SNMCs because no significant change in health status is implied. Similarly, adverse events which are isolated, treatable events that resolve and do not require chronic therapy are also not SNMCs (examples could include an uncomplicated acute urinary tract infection or a simple fracture resolved with conservative treatment and with no residual disability). In contrast, new diagnoses of rheumatoid arthritis or coronary artery disease are SNMCs because they imply a long-term change in health status and require ongoing medical management.

The eCRF will provide a field in which the investigator may designate AEs as MAEs, SNMCs, or both. Because of the significance of the designation for the subject's health, long-term medical management, and for evaluation of vaccine safety, SNMCs are expected to be substantiated diagnoses, not isolated symptoms which might or might not be an SNMC, and the investigator should record sufficient data in the source document to support the diagnosis.

Full details of MAEs and SNMCs (ie, nature, date of onset and recovery (if applicable) as well as an assessment of severity, relationship to study agent, seriousness, treatment, and outcome) will be recorded in the source documentation and captured in the eCRF, and will require the Investigator(s) causality assessment.

MAEs and SNMCs will be recorded and summarized from Day 0 to Day 21 for the unblinded data review and from Day 0 to Day 364 following study completion for the final analysis, for all subjects in the Safety Population. Note that MAEs and SNMCs are also included in the overall summary of AEs.

8.3 Serious Adverse Events

A SAE is defined as an AE that results in any of the following outcomes:

- Death,
- An immediate threat to life,
- In-patient hospitalization or prolongation of an existing hospitalization (Hospitalization is defined as an actual admission, not a 24-hour stay or emergency room visit; note that elective surgeries, undertaken for conditions present prior to receipt of study drug and without complication, should not be considered SAEs),
- A persistent or significant disability/incapacity (substantial disruption of an ability to conduct normal life functions), or
- A congenital anomaly or birth defect (not relevant to this protocol).

An important medical event that may not result in death, be life-threatening, or require hospitalization may be considered an SAE when, based upon appropriate medical judgment, it may jeopardize the patient or subject and may require medical or surgical intervention to prevent one of the outcomes listed in this definition. Examples of such medical events include allergic bronchospasm requiring intensive treatment in an emergency room or at home, blood dyscrasias or convulsions that do not result in in-patient hospitalization. Events which could have led to the above outcomes had they occurred with greater severity are not SAEs, but should be reported as AEs, MAEs, or SNMCs, as appropriate.

The eCRF will provide a field for designating an AE as SAE. SAEs are associated with enhanced reporting requirements (see protocol, Section 8.3). A listing of subjects with SAEs will be summarized from Day 0 to Day 21 for the unblinded analysis, and from Day 0 to Day 364 following study completion for the final analysis, for all subjects in the Safety Population.

8.4 Vital Signs

Descriptive statistics for vital signs (blood pressure, pulse, respiratory rate) at each visit will be presented by treatment group for all subjects in the Safety Population.

9 SAMPLE SIZE CONSIDERATIONS

The sample size is chosen as adequate for an initial description of safety and immunogenicity to direct future development and dosing. No hypothesis tests are specified and the sample size is not intended to support any statistical contrast of Tri-NIV with Fluzone HD. For safety endpoints, the probability of observing at least one adverse event among 110 subjects for each of the two Tri-NIV groups or 220 for the two Tri-NIV groups combined, are > 90% if the true rate of such events is 2.1% and 1.1%, respectively. With 110 for each of the two Tri-NIV group or 220 for the two Tri-NIV groups combined, observing no adverse events of interest (eg, vaccine-related SAE) would represent an upper bound of the one-sided 95% CI on the percentage of such events of 2.7% and 1.4%, respectively.

Tri-NIV is expected to be comparable (statistically non-inferior) to the currently licensed Fluzone HD in terms of SCR. If the underlying SRRs is 70% for both the Tri-NIV and active control groups for a given strain, with 100 subjects in each group, the trial has a 46% power to detect -0.10 non-inferiority (NI) margin. If the underlying SRR is 50%, the power will be 41%.

10 PRELIMINARY UNBLINDED AND FINAL ANALYSES

An unblinded analysis will be conducted upon completion of all Day 21 visits, which will include all available immunogenicity data through Day 21 at the time of the analysis and safety data (inclusive of clinical laboratory safety assessments) through Day 21. An unblinded review will be conducted of all available immunogenicity and safety data (including clinical assessments and concomitant medications) upon completion of all Day 21 visits. For the review, treatment codes will only be unblinded after all subjects have completed the Day 21 visit, the data are monitored, all applicable queries are resolved, and the database locked. The data and analyses provided in the review will be considered final for the material contained therein, and will not change.

In order to execute this review, a select group of study staff will be unblinded at the CRO and at Novavax. No individual unblinded at a subject treatment level will be involved in follow-up safety monitoring or immunogenicity determination. Specifically, personnel at the clinical

study site including, investigators and study staff, research site, immunology laboratory, and study subjects will remain blinded to treatment assignments until the end of study (ie, Day 385).

Since study procedures and monitoring practices will not change following the review and the study will not be terminated prematurely on the basis of these data, no decision cut points or stopping rules will be stipulated. No hypothesis testing will be performed.

Immunogenicity and safety analyses from the unblinded review may be presented in an abbreviated Unblinded CSR drafted by the Sponsor that will be submitted to regulatory authorities as needed. The final CSR will present the balance of all disposition, immunogenicity and safety data (inclusive of concomitant medications) through Day 364 (the scheduled end of study. The database will be locked and the final study report prepared, when all of the above data have been entered, reviewed, and all queries related to the data have been addressed.

The final CSR will present the balance of all immunogenicity and safety data through Day 364 (the scheduled end of study). The database will be locked and the final study report prepared, when all of the above data have been entered, reviewed and all queries related to the data have been addressed.

Full descriptions of the planned analyses are included in the SAP. Any decisions to deviate from the planned analyses will be described in detail in the final study report.

11 COMPUTER METHODS

Statistical analyses will be performed using SAS® version 9.3 or higher in a Windows environment.

Sample size calculations based on two-sample t-test were performed using PASS 12, version 12.0.3 released on August 6, 2013.

12 DATA HANDLING CONVENTIONS

All statistical analyses will be 2-tailed and assessed at the 5% significance level.

All output will be incorporated into Microsoft Word or Excel files, or Adobe Acrobat PDF files, sorted and labeled according to the International Conference on Harmonisation (ICH) recommendations, and formatted to the appropriate page size(s).

Tabulations will be produced for appropriate demographic, baseline, and safety parameters. For categorical variables, summary tabulations of the number and percentage of subjects within each category (with a category for missing data) of the parameter will be presented. For continuous variables, the number of subjects, mean, median, standard deviation (SD), minimum, and maximum values will be presented.

For all analyses, a p-value of < 0.05 will be considered statistically significant. All references to analysis of GMT will be interpreted as analysis of the log₁₀ of titer values or of the reciprocal titers (eg, the reciprocal titer of 1:160 is the number 160) or of concentrations.

The individual immunogenicity titer values recorded as below the LLoQ of the assay will be set to half LLoQ for the purposes of GMT, GMR analyses. The LLoQ values will be provided by corresponding lab or CRO as part of the data transfer.

All descriptive statistical analyses will be performed using SAS statistical software Version 9.3 or higher in a Windows environment, unless otherwise noted. Medical history and AEs will be coded using the MedDRA Version 20.0.

12.1 Baseline Definitions

For all analyses, baseline will be defined as the last non-missing measurement prior to the first administration of the study material. For immunogenicity analysis, baseline will be the sample drawn prior to the first vaccination, on the day of vaccination.

12.2 Adjustments for Covariates

Immunogenicty endpoints will not be adjusted for pre-vaccination titer.

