Several features of Tri-NIV warrant clinical investigation of its safety and immunogenicity among older adults. In ferrets, Tri-NIV administered with Matrix-M1 adjuvant elicited rapid and robust immune responses in terms of geometric mean HAI titers with responses exceeding those induced by Fluzone HD. Secondly, geometric mean 50% microneutralizing (MN) titers against a broad panel of historic H3N2 strains tested, dating to 1999 and spanning a number of clinically-significant antigenic drift events, showed 2 to 214-fold higher titers among animals given Tri-NIV with Matrix-M1 adjuvant than among animals given Fluzone HD. These data suggest that Tri-NIV may elicit antibodies to broadly-neutralizing epitopes capable of providing greater drift strain protection, even against strains such as A/HongKong/4801/2014, which are associated with impaired influenza vaccine efficacy in humans. While cross-lineage B virus antibody responses were not seen in naïve animals, the possibility of such responses should be considered, and will be evaluated, in immunologically-experienced humans.

Because Tri-NIV is produced at high yields in insect cells, it potentially presents a more costeffective method of producing large quantities of an annual seasonal influenza vaccine when compared to the traditional egg-based manufacturing processes, and if successful, may also offer a flexible and rapidly-responsive platform for production of novel influenza hemagglutinins from strains with pandemic potential. Initial development, however, will focus on potential superior benefits of a seasonal trivalent or quadrivalent formulation in the vulnerable older adult population.

Two Tri-NIV treatment groups evaluating either 15 or 60 μ g of HA antigen per strain have been proposed to 1) allow comparison with immunogenicity and safety profile of Fluzone HD and 2) evaluate the antigen dose response to inform further clinical development of the vaccine. The Matrix-M1 adjuvant, shown to remarkably enhance immunological responses of several vaccine antigens, with an overall acceptable safety profile in over 1,400 humans exposed to date, is proposed as the adjuvant of choice.

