2.2 Study Endpoints

2.2.1 Primary Endpoints

• Number and percentage (95% confidence interval [CI]) of subjects with solicited local and systemic adverse events over the 7 days post-injection (ie, Day 0 through Day 6 post-dosing); all adverse events (including adverse changes in clinical laboratory parameters) through 21 days post-injection; and MAEs, SAEs, and SNMCs through 1 year post-Day 0 dosing.

- Antibody titers specific for the HA receptor binding domains of each of the virus strains included in Tri-NIV as measured by the HAI assay. Derived/calculated endpoints based on these data will include:
 - Geometric mean titer (GMT) defined as the antilog of the mean of the log-transformed HAI titers for a given treatment group.
 - \circ Geometric mean ratio (GMR) defined as the ratio of post-vaccination and pre-vaccination HAI GMTs within the same treatment group (designated as GMR_{Post/Pre}).
 - Seroconversion rate (SCR) defined as the percentage of subjects with either a baseline HAI titer < 1:10 and a post-vaccination titer ≥ 1:40, or a baseline HAI titer ≥ 1:10 and a 4-fold increase in post-vaccination HAI titer relative to baseline.
 - Seroconversion rate difference defined as the difference of seroconversion rates between each of the Tri-NIV vaccine groups and Fluzone HD group and its upper 95% CI.
 - Seroprotection rate (SPR) defined as the percentage of subjects with an HAI titer \ge 1:40.

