3.2 Intent-to-Treat Population

The Intent-to-Treat (ITT) Population includes all subjects in the Safety Population that provide any HAI serology data. The ITT Population will be the secondary population used for any immunogenicity analyses and will be analyzed according to treatment as randomized.

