3.3 Per-Protocol Population

The Per-Protocol (PP) Population includes all subjects in the Safety Population that received the assigned dose of the test article on Day 0 according to protocol, have HAI serology results for Day 0 and Day 21, and have no major protocol deviations affecting the primary immunogenicity outcomes as determined by Novavax prior to database lock and unblinding. The PP Population will be the primary population used for immunogenicity analyses.

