7 ANALYSES ADDRESSING PROTOCOL OBJECTIVES

7.1 Analyses of Primary Objectives of immunogenicity

The analysis of primary immunogenicity endpoints will be conducted by using PP and ITT population, with PP population as the primary analysis. No missing data will be imputed.

Antibody titers specific for the HA receptor binding domains of each of the virus strains included in Tri-NIV, H1N1, H3N2, and Bv, will be analyzed.

- Geometric mean titers (GMT) of Antibody titers specific for the HA receptor binding domains of each of the virus strains and their 95% CIs will be summarized by treatment at baseline (pre-vaccination on Day 0) and post vaccination on Day 21. GMT will be calculated as the antilog of the mean of the log-transformed HAI titers for a given treatment group. Lognormal distribution is assumed for antibody titer to construct confidence interval.
- Between-group geometric mean ratio (GMR_{new/ref}) and its 95% CI for each of the Tri-NIV groups against active comparator group Fluzone HD will be conducted using two-sample t distribution. A sample SAS code is given below:

```
proc ttest data=fludata alpha=0.05;
by Visit;
class grp;
var log(HAI D21);run;
```

• Within-group geometric mean ratio (GMR_{post/pre}) for each arm will be conducted using paired t distribution. A sample SAS code is given below:

```
proc ttest data= fludata_Long alpha=0.05;
by Visit Group;
PAIRED log(HAI D21)*log(HAI D0);run;
```

Seroconversion rate (SCR) is defined as the percentage of subjects with either a baseline HAI titer < 1:10 and a post-vaccination titer ≥ 1:40, or a baseline HAI titer ≥ 1:10 and a 4-fold increase in post-vaccination HAI titer relative to baseline. The 95% confidence interval will be constructed by Clopper-Pearson method with the following sample SAS code:

```
proc freq data=fludata ;
by treatment;
tables seroconvind/ nocum norow binomial;
exact binomial;
run;
```

• Seroconversion rate difference is defined as the difference of seroconversion rates between each of the Tri-NIV vaccine groups and Fluzone HD group. The Chi-Square p-value for testing the equality of SCRs between two groups will be derived with continuity adjustment. The Newcombe method will be used to construct its 95% confidence interval with the following sample SAS code:

```
proc freq data = fludata;
tables trtan*seroconvind / riskdiff (column=2 cl=(newcombe)) chisq;
run ;
```

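### Barring adjustment for the pre-vaccination titer (SAP 12.2) forgoes available precision in the Tri-NIV/Fluzone HD Day 21 GMRs; the planned estimate remains valid

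*SAP*

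**What the plan says.** SAP 12.2 is a single sentence, without exception or reason: "Immunogenicty endpoints will not be adjusted for pre-vaccination titer".

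SAP 7.1 plans a between-group GMR with 95% CI in which each Tri-NIV group "against active comparator group Fluzone HD will be conducted using two-sample t distribution". The sample code analyses the log Day 21 titer alone. The same section runs the primary immunogenicity analyses "by using PP and ITT population, with PP population as the primary analysis. No missing data will be imputed".

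PP subjects must "have HAI serology results for Day 0 and Day 21" (SAP 3.3). The ITT set is looser: it "includes all subjects in the Safety Population that provide any HAI serology data" (SAP 3.2). The baseline sample is drawn before vaccination (SAP 12.1). Randomization is stratified by age, gender and 2016-17 influenza vaccination (SAP 1.2).

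The GMR listed as a primary endpoint is a different quantity, "the ratio of post-vaccination and pre-vaccination HAI GMTs within the same treatment group" (SAP 2.2.1). Day 0 titers enter that paired analysis and the seroconversion definition. Neither document plans an adjusted between-group GMR, even as a sensitivity analysis.

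**The concern.** Where subjects' Day 0 and Day 21 log titers are correlated, part of the Day 21 spread is predictable from a value measured before treatment. An unadjusted t leaves that part in the standard error. Adjusting for a pre-treatment covariate in a randomized comparison removes it and needs no extra data.

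What is at stake is the width of one reported CI. That comparison has a stated purpose: SAP 1 says the two Tri-NIV groups were chosen partly to "allow comparison with immunogenicity and safety profile of Fluzone HD", and SAP 9 says the sample is meant to guide later development and dosing. Because the sample size was not set for this contrast, the existing baseline data are the cheapest way to sharpen it.

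**Working it through.** **Plan figures.** The documents give no SD, correlation or expected width for this GMR. Their only Tri-NIV versus Fluzone HD power figures are in SAP 9: 46% and 41%, for non-inferiority on seroconversion with 100 per group and a margin of -0.10. They reproduce as Φ(0.10/√(2p(1-p)/n) - 1.645), that is with one-sided 5%: 45.9% at p = 0.70 and 40.9% at p = 0.50. They say nothing about the GMR.

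**Inputs from the documents.** About 110 per group, 1:1:1 (SAP 1.1, 1.2); two-sided 95% CI; 2-fold dilutions from 1:10 (Protocol 7.2.1), with values below 10 set to 5 (Protocol 10.4.1.2). I also use 100 per group, the n in SAP 9's power sentence.

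**Assumed.** SD 0.5 log10; within-group correlation r of 0 to 0.7; the effects of the strata on titer.

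**Step 1, unadjusted CI.** Half-width h = t(0.975, 2n-2) × SD × √(2/n). With n = 110, h = 0.1329 log10, so the limits lie a factor of 10^0.1329 = 1.36 either side of the GMR. With n = 100 the factor is 1.38.

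**Step 2, ideal gain from the Day 0 titer alone.** h is multiplied by √(1-r²), with a one-degree-of-freedom correction. With n = 110:

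| r | h | CI factor | Change in width |
|---|---|---|---|
| 0 | 0.1332 | 1.36 | 0.2% wider |
| 0.3 | 0.1271 | 1.34 | 4% narrower |
| 0.5 | 0.1153 | 1.30 | 13% narrower |
| 0.7 | 0.0951 | 1.24 | 28% narrower |

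**Step 3, effect of the assay scale.** With 2-fold dilutions and the half-limit rule, the simulated standard-error ratios for the same one-covariate model were 1.00 / 0.96 / 0.88 / 0.75 at r = 0 / 0.3 / 0.5 / 0.7, against 1 / 0.95 / 0.87 / 0.71 in theory. Discreteness trims the gain but does not remove it.

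**Step 4, the model proposed below.** ANCOVA on Day 0 titer and the three stratification factors with HC3 standard errors, against an unequal-variance t; n = 100, SD 0.5. CI width ratios, adjusted over unadjusted, by simulation:

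| Assumed stratum effects | r = 0 | 0.3 | 0.5 | 0.7 |
|---|---|---|---|---|
| None (range over runs) | 1.011-1.017 | 0.969-0.975 | 0.889-0.895 | 0.752-0.757 |
| Modest | 1.005 | 0.964 | 0.885 | 0.747 |
| Large (-0.2, 0.1, -0.2 log10) | 0.976 | - | - | - |

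With modest effects the CI factor falls from 1.38 to 1.37 / 1.33 / 1.27 at r = 0.3 / 0.5 / 0.7. The equivalent unadjusted sample, 100/ratio², is 108 / 128 / 179 per group. With no stratum effects (ratios 0.975 / 0.895 / 0.757) it is 105 / 125 / 175.

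**Step 5, robustness.** With modest stratum effects, moving the Day 0 mean to 1.2 or 1.8 log10 gave ratios of 0.962-0.966 / 0.880-0.893 / 0.739-0.770, so the gain at r = 0.7 can be as low as 23%. Coverage of the HC3 interval was 0.938-0.963 over all runs; that of the t interval was 0.939-0.963 where both were recorded. With unequal arm SDs (0.4 and 0.6), an ANCOVA with one pooled variance covered only 0.929-0.940 in the affected comparisons, which is why the variance method must be named.

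**The case against.** The strongest reply is that nothing is broken. SAP 12.2 is an explicit, pre-specified choice and SAP 7.1 follows it. The objectives are descriptive, "the sample size is not intended to support any statistical contrast of Tri-NIV with Fluzone HD" (SAP 9), and no decision threshold hangs on this CI. The between-group GMR is not a listed endpoint, and Protocol 10.4.1.2 does not plan it: its between-group intervals are for seroconversion and seroprotection differences only. All of that stands and limits the weight. It does not remove the point, because SAP 7.1 will report the GMR with its CI.

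Three practical objections also stand and are met in the fix:
- The adjusted GMR will not equal the ratio of the displayed GMTs.
- Protocol 7.2.1 adds a recombinant-antigen HAI assay for at least H3N2, so a strain may have more than one readout, and the PP definition does not require paired results for each strain and assay.
- SAP 12.2 concerns only the titer, whereas the model adds the strata. The Day 0 titer supplies almost all of the gain when stratum effects are nil or modest; the strata are included because the randomization used them.

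A reader might infer more than the documents support:
- **That the unadjusted GMR is biased or its CI invalid.** Randomization makes it unbiased.
- **That the trial is underpowered against Fluzone HD.** It was not sized for that contrast.
- **That the plan contradicts itself because the Protocol change history mentions ANCOVA.** That wording concerned the within-group GMR and was replaced by a paired t-test.
- **That Day 0 titers are complete in every analysis.** ITT subjects may lack one, and microneutralization may be run on a subset.

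**Conclusion.** The point holds as an optional efficiency improvement to one analysis, the between-group Day 21 HAI GMR in the PP set. Its size cannot be derived from the documents. Under the assumed range and nil to modest stratum effects, the log-scale CI is about 2-4% / 10-12% / 24-26% narrower at correlations of 0.3 / 0.5 / 0.7. At 0.3 that is small; at 0.5 or more it is worth having. At correlation 0 the price is a CI about 0.5-2% wider if the strata predict weakly or not at all, and none if they predict strongly. The percentages rest on the assumed correlation, stratum effects and baseline level; the fold factors rest also on SD 0.5 log10 and the n used.

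**What to change.** Before the Day 21 unblinded review, amend SAP 12.2 and 7.1 as follows.

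- For each vaccine strain, in PP subjects with both titers for that strain in the validated egg-antigen HAI assay, take each Tri-NIV/Fluzone HD GMR and its 95% CI from an ANCOVA of log10 Day 21 titer on treatment, log10 Day 0 titer, age stratum, gender and 2016-17 vaccination.
- Name HC3 standard errors as the single variance method.
- Apply the same model separately to any additional H3N2 recombinant-antigen readout.
- Show the unadjusted GMR alongside, with a footnote that the adjusted GMR will not equal the ratio of the displayed unadjusted GMTs.
- Run the ITT version on subjects with both titers, since nothing is imputed.
- Leave GMTs, within-group GMRs, seroconversion and seroprotection as planned.

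The cost is wording in two SAP sections, one model per strain and readout, four covariate degrees of freedom and one footnote. No new data are needed: the Day 0 titers and strata are already collected.
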